Clinical Trial Document Cover Page

Official Title:

Impact of TruNatomy and ProTaper Gold Ni-Ti Systems Using Resin-Based or Bioceramic Sealers on Postoperative Pain After Root Canal Treatment: A Randomized Clinical Trial

Acronym:

POP

NCT Number:

NCT07526844

Document Type:

Study Protocol and Consent Form

Date:

April 15, 2026

Institution:

Faculty of Dentistry
European University of Lefke

Asst. [name]. [name]

<[name]>

Impact of Trunatomy and Protaper Gold Ni-Ti Systems Using Resin-Based or Bioceramic Sealers on Postoperative Pain After Root Canal Treatment: A Randomized Clinical Trial

Introduction

Postoperative pain following root canal treatment is a critical factor influencing both clinical success and patient comfort. Despite advances in endodontic techniques, pain after treatment remains a common concern and may negatively affect patient perception of care (1, 2).

Postoperative pain is multifactorial in origin and may result from microbial, chemical, and mechanical factors. Microbial causes include residual infection due to inadequate chemo-mechanical preparation or coronal leakage. Chemical factors involve the use of irrigants, intracanal medicaments, and obturation materials. Mechanical factors include apical extrusion of debris, irrigants, and microorganisms, as well as trauma to periapical tissues during instrumentation (1, 2).

Among these factors, the root canal preparation technique plays a crucial role in the development of postoperative pain. TruNatomy (Dentsply Maillefer, Ballaigues, Switzerland) is a recently introduced rotary system designed for minimally invasive canal shaping. Its slim design and regressive taper allow preservation of dentin and natural canal anatomy, which may reduce apical extrusion of debris and postoperative discomfort (1).

In contrast, ProTaper Gold (Dentsply Maillefer, Ballaigues, Switzerland) is a widely used rotary system characterized by a progressive taper and enhanced cutting efficiency. While effective in shaping complex canal anatomies, its more aggressive design may result in increased debris extrusion, potentially contributing to postoperative pain (3).

The type of root canal sealer is another important factor influencing treatment outcomes. Sealer extrusion into periapical tissues may induce inflammatory reactions depending on its chemical composition. The chemical composition of sealers also influences the degree of tissue response (4, 5). AH Plus (Dentsply DeTrey, Konstanz, Germany), an epoxy resin-based sealer, is known for its excellent sealing ability and dimensional stability. In contrast, TotalFill BC Sealer (FKG Dentaire SA, La Chaux-de-Fonds, Switzerland), a calcium silicate-based bioceramic sealer, demonstrates favorable biocompatibility and bioactivity through calcium ion release (6).

The aim of this study is to evaluate the effect of two rotary file systems (TruNatomy and ProTaper Gold) used in combination with two different sealers (AH Plus and TotalFill BC) on postoperative pain in patients with asymptomatic irreversible pulpitis.

The null hypothesis is that neither the instrumentation system nor the sealer type, nor their interaction, has a significant effect on postoperative pain.

Methods

This study is designed as a prospective, randomized clinical trial. Ethical approval was obtained from the European University of Lefke Ethics Committee (Protocol No: BAYEK057.03).

Sample Size Calculation

A total of 180 patients will be recruited and randomly allocated into four groups ($n = 45$ per group). Considering an anticipated dropout rate of approximately 20%, the final analyzable sample size is expected to be 144 patients (36 per group).

This sample size provides 80% power to detect a moderate effect size (Cohen's $d \approx 0.42$) and 90% power to detect a larger effect ($d \approx 0.48$) at a significance level of 5%. It also allows evaluation of potential interaction effects between the instrumentation system and sealer type.

Patient Selection

Patients will be recruited from individuals referred to the European University of Lefke Dental Clinic for root canal treatment. Only mandibular first and second premolars diagnosed with asymptomatic irreversible pulpitis will be included. This condition is defined as inflamed vital pulp tissue without clinical symptoms, caused by caries, caries removal, or trauma (7).

Written and verbal informed consent will be obtained from all participants prior to treatment (Appendix 1). An electronic questionnaire including the Numerical Rating Scale (NRS) and analgesic intake will be sent to patients (Appendix 2). Patients will be contacted by phone and asked to complete the questionnaire online. Submitted responses will not be editable. The primary outcome will be postoperative pain, while secondary outcomes will include analgesic consumption and flare-up incidence.

Inclusion Criteria

- Asymptomatic teeth with delayed positive response to thermal and electric pulp testing
- Vital teeth with signs of irreversible pulpitis
- Mature mandibular first or second premolars
- Periodontally healthy teeth

Exclusion Criteria

- Patients with systemic conditions (e.g., diabetes, immunocompromised status, pregnancy)
- Antibiotic use within the past month
- Use of analgesics within 7 days prior to treatment
- Known allergy to materials used
- Teeth with periapical lesions
- Non-vital or symptomatic teeth
- Teeth requiring post-core restorations
- Calcified canals, root resorption, or immature teeth

Randomization and Blinding

Participants will be randomly assigned to one of four groups using a computer-generated randomization sequence. Allocation concealment will be ensured using sealed opaque envelopes.

Patients and outcome assessors will be blinded to group allocation. Due to the nature of the intervention, the operator could not be blinded.

A total of 180 sealed envelopes containing combinations of TruNatomy or ProTaper Gold systems and AH Plus or TotalFill BC sealers will be prepared and mixed in an opaque container. Each patient will select one envelope, which determines the assigned group. To minimize bias, the operator will open the envelope only after gaining access to the root canal.

Treatment Protocol

All procedures will be performed by a single experienced clinician in a standardized clinical setting, using the same irrigation solutions and obturation techniques, and completed in a single visit.

Inferior alveolar nerve block anesthesia will be administered using 2% articaine hydrochloride with 1:80,000 epinephrine (Jetokain; Adeka). After rubber dam isolation, caries and old restorations will be removed, and standard access cavities will be prepared.

Working length will be determined using an electronic apex locator (Raypex 6; VDW) and confirmed radiographically. Glide path preparation will be performed using size 8–10 K-files, and apical patency will be confirmed with a size 10 K-file.

Root Canal Shaping

- **TruNatomy Groups (Groups 1–2):**
Preparation will be performed at 500 rpm and 1.5 Ncm torque using TruNatomy Glider (17/0.02) followed by Prime file (26/0.04).
- **ProTaper Gold Groups (Groups 3–4):**
Preparation will be performed at 300 rpm and 2 Ncm torque using ProGlider followed by SX, S1, S2, F1, and F2 files.

Irrigation with 2.5% NaOCl will be performed using a 30-gauge side-vented needle. Final irrigation will include activated NaOCl (EndoActivator), EDTA, distilled water, and 2% chlorhexidine.

Obturation

Modified single-cone technique will be used:

- Group 1: TruNatomy + AH Plus
- Group 2: TruNatomy + TotalFill BC
- Group 3: ProTaper Gold + AH Plus
- Group 4: ProTaper Gold + TotalFill BC

Excess gutta-percha will be removed and compacted below CEJ, followed by composite restoration (Filtek Z250; 3M ESPE).

Postoperative Pain Assessment

Primary Outcome

Postoperative pain will be evaluated at different time points—6, 12, 24, 48, and 72 hours, as well as on the 7th day—using the Numerical Rating Scale (NRS). The NRS is a numerical version of the Visual Analog Scale (VAS), ranging from 0 (no pain) to 10 (unbearable pain) (8, 9). It will be explained to participants as follows:

- No pain (0)
- Mild pain (1–3): Low-level pain that does not require analgesics
- Moderate pain (4–6): Tolerable pain that can be controlled with analgesics\
- Severe pain (7–10): Unbearable pain that is not adequately controlled by analgesics and often requires rest

Postoperative Analgesic Protocol: All patients will be prescribed 400 mg ibuprofen and will be advised to use it only in cases of severe pain. Analgesic intake will be recorded.

Follow-up Visits: Follow-up visits will be scheduled on the 7th day to clinically confirm patient-reported outcomes.

Statistical Analysis

Data will be analyzed using appropriate statistical software. Statistical significance will be set at $p < 0.05$.

References

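### The stated power (80% at d≈0.42, 90% at d≈0.48) fits all 180 recruited patients; for the 144 expected to be analysed, a conventional two-sided main-effect test gives about 71% and 82%

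*Protocol*

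**What the plan says.** All the figures are in one place: Protocol, Methods, Sample Size Calculation.

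- Recruitment: "A total of 180 patients will be recruited and randomly allocated into four groups ($n = 45$ per group").
- After a dropout allowance of about 20%, "the final analyzable sample size is expected to be 144 patients (36 per group").
- The next sentence makes the power claim: "This sample size provides 80% power to detect a moderate effect size (Cohen's $d \approx 0.42$) and 90% power to detect a larger effect". It puts the larger effect at d≈0.48 and the significance level at 5%.

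The section does not say whether the test is one- or two-sided, or which comparison the power refers to. The null hypothesis at the end of the Introduction is that "neither the instrumentation system nor the sealer type, nor their interaction, has a significant effect on postoperative pain". The Statistical Analysis section repeats the 5% level and adds nothing on sidedness.

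**The concern.** The power sentence directly follows the sentence that sets the analysable sample at 144, so a reader takes the 80% and 90% to be what 144 patients deliver. If the figures were computed for 180 patients, the loss of a fifth of the sample has been stated but not applied.

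This is the only sample-size justification in the protocol, and it concerns the primary outcome. At d=0.42 the chance of missing a true effect would be about 29% (100% − 71%), against the 20% implied. A null result could then be taken as firmer evidence against a moderate effect than the trial can give.

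**Working it through.** **Inputs (Sample Size Calculation, unless marked).**
- Recruited: 180, or 45 in each of four groups. Each level of a factor pools two groups: 2 × 45 = 90.
- Dropout about 20%: 180 × 0.80 = 144, or 36 per group. Each level of a factor has 2 × 36 = 72.
- Stated: 80% power at d≈0.42 and 90% at d≈0.48, at the 5% level.
- Assumed: two-sided test, because the null hypothesis is non-directional.
- Assumed: one factor's main effect, half the sample against the other half, because Cohen's d is a two-group measure.
- Assumed: one measurement per patient and equal groups.

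**Formulas (normal approximation, n patients per level).**
- Detectable effect: d = (1.960 + z_power) × √(2/n), with z = 0.842 for 80% and 1.282 for 90%.
- Power = Φ(d × √(n/2) − 1.960).

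**Step 1: reproduce the stated figures with n = 90.** √(n/2) = √45 = 6.708.
- Detectable d at 80%: 2.802 / 6.708 = 0.418.
- Detectable d at 90%: 3.242 / 6.708 = 0.483.

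These round to the stated 0.42 and 0.48. The t-based values are 0.420 and 0.486.

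**Step 2: the expected analysable sample, n = 72.** √(n/2) = √36 = 6.
- Detectable d at 80%: 2.802 / 6 = 0.467.
- Detectable d at 90%: 3.242 / 6 = 0.540.
- Power at d=0.42: Φ(2.52 − 1.96) = Φ(0.56) = 71.2%.
- Power at d=0.48: Φ(2.88 − 1.96) = Φ(0.92) = 82.1%.

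**Step 3: check with exact tests.** The noncentral t test and the 1-df F test in a 2×2 analysis agree to one decimal place.

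| Two-sided 5%, main effect | Power at d=0.42 (normal / exact) | Power at d=0.48 (normal / exact) | Detectable d, 80% / 90% (t-based) |
|---|---|---|---|
| 180 patients (90 vs 90) | 80.4% / 80.0% | 89.6% / 89.3% | 0.420 / 0.486 |
| 144 patients (72 vs 72) | 71.2% / 70.6% | 82.1% / 81.6% | 0.470 / 0.544 |

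The shortfall against the stated power is about 9 points at d=0.42 and 8 points at d=0.48.

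**Step 4: could a one-sided 5% test at 144 explain the figures?** Replace 1.960 with 1.645.
- Power: Φ(2.52 − 1.645) = 80.9% and Φ(2.88 − 1.645) = 89.2% (t-based 80.6% and 88.9%).
- Detectable d: 0.414 and 0.488 (t-based 0.416 and 0.490).

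The power comes close, but the 90% effect rounds to 0.49, not 0.48. Under the normal approximation the ratio of the 90% to the 80% detectable effect does not depend on n. It is 3.242/2.802 = 1.157 two-sided and 2.926/2.487 = 1.177 one-sided. Values that round to 0.42 and 0.48 allow a ratio of at most 0.485/0.415 = 1.169, which admits the two-sided test and excludes the one-sided one.

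**The case against.** The strongest objection is that the basis of the calculation is inferred, from two rounded figures marked as approximate. Four arguments follow from this.

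- **One-sided test.** At 144 it gives about 81% and 89%, and the Introduction's rationale for the file systems leans in one direction. However, the null hypothesis is non-directional and includes an interaction, and no one-sided test appears anywhere. The ratio argument also counts against it, though with approximate figures it is evidence and not proof.
- **Repeated measures.** Pain is scored at six time points. If the analysis used the mean of six equally correlated scores, the variance would shrink by (1 + 5ρ)/6. At ρ = 0.75 that is 0.79, and the detectable effects at 144 become 0.467 × √0.79 = 0.415 and 0.540 × √0.79 = 0.481, in line with the stated pair. The protocol gives no correlation and does not name such a summary, so this cannot be credited as the basis. It does show that the 71% and 82% depend on one measurement per patient.
- **Reference to 180.** If the power sentence points back to the recruited number, its arithmetic is right. It then describes complete follow-up, which the preceding sentence says is not expected.
- **Dropout may be smaller.** Follow-up lasts only seven days. With less dropout, power would lie between the two rows of the table. The 20% is nevertheless the protocol's own planning figure.

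What stands is that the conclusion must be conditional on the stated test. None of these arguments reconciles the power figures with the 144 from what the protocol itself says.

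**Conclusion.** The point holds in conditional form. For a two-sided 5% comparison of two means on one factor's main effect, with equal groups and one measurement per patient, the stated power is that of 180 patients. The protocol expects to analyse 144, for whom power is about 71% at d≈0.42 and 82% at d≈0.48. The effects detectable with 80% and 90% power are about 0.47 and 0.54, which is 0.05 to 0.06 SD larger than stated.

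A reader might infer two stronger things that the protocol does not support:
- **That 71% and 82% are the trial's true power without qualification.** Sidedness and contrast are inferred, and the analysis of the six time points is not described.
- **That the protocol overstates its power for comparing single groups of 36.** It claims no power for such comparisons: the per-group figure is a head count, and the null hypothesis concerns factor effects and their interaction.

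**What to change.** Restate the power for the analysable sample and name its basis. If the sponsor confirms a two-sided test of the main effects, suitable wording would be:

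> With 144 analysable patients (72 vs 72 for each main effect, two-sided 5%), the trial has 80% power for d≈0.47 and 90% power for d≈0.54. These figures apply to the two main effects, file system and sealer.

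If the calculation rested on something else, such as a summary over time points with an assumed correlation, the paragraph should state that basis and its inputs, again for 144 patients.

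The cost is one paragraph and a slightly less favourable stated effect. Recruitment, randomisation and analysis stay as they are. Keeping 80% power at d=0.42 on the two-sided basis would need 180 analysable patients, hence 180 / 0.8 = 225 recruited; correcting the statement does not require this.

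### A single envelope tells the unblinded operator the sealer before shaping, although no step before obturation depends on it

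*Protocol*

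**What the plan says.** Randomization and Blinding describes "180 sealed envelopes containing combinations of TruNatomy or ProTaper Gold systems and AH Plus or TotalFill BC sealers", mixed in an opaque container. It continues: "Each patient will select one envelope, which determines the assigned group". One draw by the patient thus fixes both factors. On timing it says: "To minimize bias, the operator will open the envelope only after gaining access to the root canal".

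On blinding, the same section says: "Patients and outcome assessors will be blinded to group allocation". For the clinician it says: "Due to the nature of the intervention, the operator could not be blinded". That statement draws no distinction between the two factors or between stages of treatment. No second envelope or staged disclosure of the sealer is described.

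Treatment Protocol adds: "All procedures will be performed by a single experienced clinician in a standardized clinical setting, using the same irrigation solutions and obturation techniques".

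**The concern.** The trial tests two factors and their interaction, and the null hypothesis names all three effects. The two factors enter the procedure at different times. The operator has to know the file system in order to shape the canal, but has to know the sealer only in order to fill it. The stated reason for leaving the operator unblinded therefore covers the file during shaping and the sealer at obturation. It does not cover the sealer during shaping and irrigation.

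If the operator knows which sealer will follow, care in the earlier steps could vary with it, consciously or not. The Introduction gives a possible motive: it says that extruded sealer may inflame the periapical tissues to a degree that depends on its chemistry, and it describes the bioceramic sealer as favourably biocompatible. Any resulting difference in pain would be attributed to the sealer. If it arose more with one file system than with the other, it would appear as an interaction. Because one clinician treats everyone, such a habit could not average out over operators, and a larger sample would not reduce it.

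**Working it through.** No figure in the Protocol bears on this point, so there is nothing to reproduce or recompute. The check sets the order of steps against the moment of disclosure.

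**Inputs.** Envelope content and opening time come from Randomization and Blinding; the steps from Treatment Protocol, Root Canal Shaping and Obturation; the tested effects from the null hypothesis; the causes of pain from the Introduction.

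**Sequence, assuming the steps are done in the order listed.**

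| Step | Differs by file system? | Differs by sealer? | Sealer needed? |
|---|---|---|---|
| Access cavity | No | No | No |
| *Envelope may be opened from here* | | | |
| Working length | No | No | No |
| K-file glide path and patency | No | No | No |
| Rotary shaping (2 instruments in Groups 1–2, 6 in Groups 3–4) | Yes | No | No |
| Irrigation, including final irrigation | No | No | No |
| Obturation | Groups 1–2 against 3–4 | Groups 1 and 3 against 2 and 4 | Yes |

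The text on the K-file step makes no mention of group: "Glide path preparation will be performed using size 8–10 K-files, and apical patency will be confirmed with a size 10 K-file".

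**Reasoning.**

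1. The opening rule sets an earliest moment, not a latest one. If the envelope is opened as soon as access is gained, the sealer is known through four rows of the table before it is needed.
2. If the operator waits as long as the single envelope allows, it must still be opened before rotary shaping, because the file system is in it. The sealer is then still known through shaping and irrigation. Timing alone cannot solve this while both factors share one envelope.
3. Shaping and irrigation are the stages at which the causes named in the Introduction would arise: debris, irrigant and organisms pushed past the apex, and injury to periapical tissue by instruments.
4. The exposure covers every participant. The sealer contrast compares two groups of 45 with two groups of 45, so 45 + 45 = 90 per sealer as randomised and 36 + 36 = 72 per sealer in the expected analysable sample. The interaction uses all four groups.
5. A lesser point follows for the file system. Opening at access reveals it before working length, glide path and patency, which are common to all groups. Its disclosure can wait until rotary shaping, but no later.

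**The case against.** The strongest reply is that this is a possible refinement and not a misstatement. For the treatment as a whole the operator indeed cannot be blinded, since that person handles the files and places the sealer. The Protocol promises no partial blinding that it then breaks. Opening after access already keeps the assignment hidden at enrolment and during access preparation.

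The text also has real safeguards. Working length is measured electronically and checked on a radiograph. K-file sizes, rotary sequence, speed, torque, needle gauge and irrigants are specified. Treatment takes a single visit, with the same irrigants and obturation technique in all groups. Pain is reported by blinded patients on a form that they cannot edit once submitted.

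Most of this stands, and it limits the weight of the point. It does not dispose of it. Irrigant volumes and times are not stated, nor is the handling of files near the apex, so some discretion remains. Blinding patients and assessors protects how pain is reported; it does not protect against differences in treatment that cause real differences in pain.

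A reader might go further and infer that the sealer comparison is biased or fully confounded with operator behaviour. The documents show an opportunity only: no operator preference, no direction and no observed difference in care. Confounding would follow only if such a habit existed. Nor does the Introduction list working length or patency as causes of pain; a link from those steps to pain is inference.

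**Conclusion.** The point holds as an avoidable opportunity for performance bias in the sealer main effect and the interaction. It arises because one envelope releases both factors before the sealer is needed. It is not a failure of allocation concealment, and the documents do not show that bias will occur. Its size and direction cannot be estimated from them.

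The conclusion rests on two assumptions: that the steps follow the order in which the Protocol lists them, and that no staged disclosure is used beyond what is written. It does not depend on the sample size or power figures.

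A reader might also infer that staged opening would remove performance bias for the sealer. It would not. The operator must know the sealer while placing it, and the Introduction names extrusion of sealer as a route to inflammation. Only the exposure before obturation can be removed. The point is a cheap improvement, not a fault that undermines the design.

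**What to change.** Keep the draw by the patient as it is, but make each envelope two-part:

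- A file-system card, opened just before rotary shaping, after working length, glide path and patency.
- A sealed opaque inner envelope with the sealer card, opened only after final irrigation is complete.
- Both opening times recorded for each patient, so that adherence can be checked.

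Replace the sentence on operator blinding with one saying that the operator learns the file system at rotary shaping, is unaware of the sealer until obturation, and is unblinded from then on.

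The cost is 180 inner envelopes, one changed sentence, a note of two times per patient, and one extra opening step at the chairside with both sealers at hand. Groups, allocation ratio, sample size, materials and treatment steps stay as they are. The change cannot be applied to patients already treated, so it should be made before recruitment or as early as possible.

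### The envelope is probably opened before working length, glide path and patency are complete, so a borderline calcified-canal decision could be made with the assignment known

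*Protocol*

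**What the plan says.** Under Randomization and Blinding, each patient draws an opaque sealed envelope that fixes both file and sealer. To limit bias, "the operator will open the envelope only after gaining access to the root canal". The same section says: "Due to the nature of the intervention, the operator could not be blinded". Under Treatment Protocol, "All procedures will be performed by a single experienced clinician".

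Treatment Protocol then gives the order of work:

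- The tooth is isolated and opened: "caries and old restorations will be removed, and standard access cavities will be prepared".
- Next comes measurement of the length of the canal, first electronically and then by radiograph.
- The last step common to all groups is stated thus: "Glide path preparation will be performed using size 8–10 K-files, and apical patency will be confirmed with a size 10 K-file".

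Only afterwards, under Root Canal Shaping, do the groups diverge by file. They diverge by sealer under Obturation.

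Exclusion Criteria lists "Calcified canals, root resorption, or immature teeth". The protocol does not say how or when calcification is judged. It does not require eligibility to be closed before the envelope is opened, and it has no rule for a canal that proves impossible to negotiate.

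**The concern.** Delaying the opening is a sound safeguard, because every eligibility check made before it is made blind to group. The safeguard appears to stop a few steps short. Passing small K-files to length is a direct test of whether a canal is open, and on the natural reading it happens after the assignment is known.

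The person passing those files also knows whether two trial instruments will follow (TruNatomy Glider and Prime) or six (ProGlider, SX, S1, S2, F1 and F2). It is plausible, though not documented, that the threshold for calling a narrow canal calcified would then differ between file systems. If such patients left the trial at different rates, and their pain differed from that of patients kept, the file comparison would no longer rest on randomisation alone. An analysis plan can define who is analysed, but it cannot conceal again an assignment that the operator has already seen.

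**Working it through.** **Sequence**

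| Step | Section of the protocol | Same in all groups? | Needs the assignment? |
|---|---|---|---|
| Access cavity | Treatment Protocol | yes | no |
| Envelope opened (natural reading) | Randomization and Blinding | – | – |
| Working length | Treatment Protocol | yes | no |
| K-file glide path, patency | Treatment Protocol | yes | no |
| Trial files | Root Canal Shaping | no | yes |
| Sealer | Obturation | no | yes |

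The system-specific gliders appear only under Root Canal Shaping, so the K-file steps need no trial instrument. The assignment is first needed at shaping, and opening could move to that point without changing any treatment step.

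**The plan's own numbers**

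Sample Size Calculation gives 180 patients, 45 per group, with about 20% loss: 180 × (1 − 0.20) = 144, or 36 per group. This reproduces. Pooled over sealers, each file arm has 2 × 45 = 90 patients randomised and 2 × 36 = 72 expected in the analysis.

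**Illustration of size (assumed inputs)**

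The documents give no removal rate, no pain difference for removed patients and no SD. Let *f* be the share of a file arm removed after opening, and *g* the difference in mean pain, in SD units, between those removed and those kept.

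- Shift in one arm's mean = *f* × *g*.
- Bias in the file contrast = *f*₁*g*₁ − *f*₂*g*₂, which is zero when removals are alike in both arms.

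The table takes removals in one arm only, which is the unfavourable case. With 72 per arm, the standard error of the difference is √(2/72) = 0.167 SD. If there is no true file effect, the two-sided 5% test rejects with probability 1 − Φ(1.96 − *fg*/0.167) + Φ(−1.96 − *fg*/0.167).

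| *f* | *g* (SD) | Shift *fg* (SD) | Type I error |
|---|---|---|---|
| 0.02 | 0.5 | 0.010 | 5.0% |
| 0.02 | 1.0 | 0.020 | 5.2% |
| 0.05 | 0.5 | 0.025 | 5.3% |
| 0.05 | 1.0 | 0.050 | 6.0% |
| 0.10 | 0.5 | 0.050 | 6.0% |
| 0.10 | 1.0 | 0.100 | 9.2% |

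Of 90 patients, 2–10% is about 2 to 9. Set against the smaller effect size in the sample size section, d = 0.42, the shift runs from 0.01/0.42 = 2% to 0.10/0.42 = 24%. With an assumed SD of 2 NRS points, it is 0.02 to 0.20 points.

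**The case against.** The strongest reply is that the sequence is inferred. The protocol uses one phrase for making the access cavity and another for reaching the root canal, and the second could mean that the canal has already been entered. That stands as an ambiguity. It is itself a reason to define the moment of opening, and even the later reading does not tie opening to completed patency.

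Calcification may also be judged on a pre-operative radiograph or at access. The criterion sits in one line with root resorption and immature teeth, which suggests selection before treatment. This stands too: a reader might infer that calcification can be known only at negotiation, but no section says so. At most, a residual set of canals missed earlier is at issue.

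Three other inferences are tempting and fail:

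- *That pulp vitality is also judged with the group known.* The exclusion of "Non-vital or symptomatic teeth" might suggest this. The pulp is seen when the chamber is opened, which comes before the envelope, so the present timing already protects that check.
- *That the plan lets the operator drop patients.* Nothing permits removal or replacement after opening, and rules for handling such cases may stand in an analysis plan that is not shown.
- *That each removal cuts into the 36 per group expected for analysis.* The plan already allows 45 − 36 = 9 losses per group, or 18 per file arm. Two to nine removals in one file arm fit within that unless other dropout uses it up.

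Finally, all inputs to the illustration are assumed, and it places every removal in one arm. That is correct, and is why it shows a range rather than an estimate.

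**Conclusion.** The point holds as one about timing and concealment. The opening moment is loosely defined and probably earlier than it needs to be. As a result, the last practical check on one exclusion criterion may be made by an unblinded operator who knows the group. This is an unguarded opportunity, not a stated procedure, and the documents do not show that biased exclusions will occur.

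Under the assumed inputs the effect runs from negligible to modest: 0.01–0.10 SD, with type I error of about 5.0–9.2%. It vanishes if removals are alike in both arms. The case for change rests less on this size than on how easily the exposure can be removed. The conclusion depends on reading access as completion of the access cavity, and on some calcified canals escaping earlier detection.

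**What to change.** Reword the sentence on opening in Randomization and Blinding, for example:

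> The operator opens the envelope immediately before group-specific shaping. By then working length, glide path and size 10 K-file patency have been completed, and the operator has recorded that all eligibility criteria are met, including the calcified-canal exclusion. A tooth found ineligible before this point is logged as a screen failure and its envelope is returned unopened. Every patient whose envelope is opened counts as randomised and is accounted for in the assigned group.

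No treatment step changes. Opening moves a few minutes later within the same visit, and screen failures before randomisation must be logged. Returning unopened envelopes keeps the set available for the 180 patients to be randomised.
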